#### **Study Protocol**

# A. Study Rationale

Twenty-nine million Americans suffered from type 2 diabetes (T2DM) in 2012 (2014 National Diabetes Report), with fewer than half able to meet treatment goals and considerably more are at risk for development of T2DM (1). Implementation of healthy eating behavior has been identified as a barrier to T2DM treatment and efficacy (2). The determinants of eating behavior and weight regulation involve a complex interaction among individual-level homeostatic, hedonic, and genetic systems, and the external food environment (3,4). The high prevalence of obesity and T2DM suggests hedonic motivation to consume food overrides homeostatic satiation signaling, resulting in excess food intake. Elevated intake increases body mass and promotes T2DM incidence via dysregulation of GLP1, amylin, and adiponectin, which in turn can negatively impact T2DM treatment options. Use of a pharmaceutical, such as bromocriptine, to aid in behavioral change is a novel method for treating and ameliorating T2DM and warrants investigation given that previous work has shown reward response to food images mediates T2DM control (5). Use of fMRI techniques to predict and evaluate hedonically-motivated eating behavior can be used to measure sensitivity to reward, and the role it plays in developing obesity (6,7), and is therefore an excellent tool to examine the associations among bromocriptine, satiety hormones, reward sensitivity and eating behavior. Moreover, since 20 35% of the population carries the DRD2 TagIA A1 allele (8), and 65% of the population is overweight or obese and at high risk for T2DM development or currently diagnosed, as much as 23% of the population may greatly benefit from dopamine agonist treatment (9). Despite the possibility that bromocriptine may have robust impact on T2DM treatment or as prevention therapy in those that are genetically predisposed, few data are available that directly examine the three systems (homeostatic, hedonic, genetic) available to assess whether a geneticallyinformed, personalized T2DM treatment is viable.

#### B. Study Objectives

**Aim 1**: To test the hypothesis that acute bromocriptine administration will alter neural and perceptual hedonic drivers of eating behavior (Visual analog scales), both contributing to a decrease in palatable food intake in those at high risk for T2DM. We expect that bromocriptine will increase BOLD response during palatable food intake in dopaminergic brain regions thought to encode reward and increase perceptual hedonic food ratings. We also expect that bromocriptine will result in decreased ad lib palatable food intake.

**Aim 2**: Test whether the A1 variant of the DRD2 TaqIA polymorphism, which is associated with reduced dopamine-D2 receptor density and dopamine signaling, moderates the impact of bromocriptine on neural and perceptual hedonic drivers of eating behavior. By testing the bromocriptine by TaqIA allele status interaction, we expect that the effects described in aim 1 will be pronounced in those with at least 1 A1 variant of the TaqIA polymorphism.

Exploratory Aim 1: To test the hypothesis that acute bromocriptine administration will alter the homeostatic mechanisms of satiation (meal termination). We expect bromocriptine to modify endocrine-mediated satiation signaling via suppressed prolactin, augmented adiponectin, amylin, glucagon like peptide-1 (GLP1), and decrease postprandial plasma glucose and insulin.

# C. Study Design

This within-subject pilot study will look at 180 overweight/obese (25 < BMI < 35) adults ages 18-35 years of age. All participants will be screened at the first visit for 50 eligible participants who will complete the other visits. 25 participants will have the DRD2 TaqIA A1 allele and 25 will have the A2/A2 variant. The study will be completed over two testing visits with a two-week washout period in between. Following published reports of the effect of acute administration of bromocriptine (10), participants will be given a 1.6mg dose of either bromocriptine-QR (Cycloset) or a placebo after a 6-8 hour fast, paralleling the recommended dosage and time of administration (11). Order of agonist/placebo will be counterbalanced across the two visits. At both visits, the participant will have a fasting blood draw, anthropometric measurements, complete visual analogue scales (VAS) for hunger, and satiety and surveys. Once bromocriptine/placebo is metabolically active (~60 mins) subjects will undergo a functional MRI with our milkshake receipt paradigm and a resting state MRI to assess functional connectivity. The Biomedical Research Imaging Center (BRIC) is located on the UNC-CH campus and 7-10 min walk from our laboratory (Neuropsychology of Ingestive Behavior Laboratory). Post-MRI, subjects will consume a fixed portion of milkshake (12 fl oz) and perform VAS hedonic ratings; will complete a test of reaction time and behavioral impulsivity, and two postprandial blood draws (30 & 60mins post milkshake ingestion). Finally, subjects will perform perceptual hedonic assessments of palatable foods and given the opportunity for ad lib consumption.

## D. Study Duration, Enrollment and Number of Subjects

For each participant, the study will include three visits on three separate days.

Total study duration will be approximately two years.

We will recruit and screen 180, 18-35-year-old overweight/obese individuals in order to enroll 50 participants with and without the presence of the DRD2 TaqIA A1 allele, and at high risk for T2DM by virtue of HbA1c. The n=42 represents the number of participants who will provide usable data and accounts for possible attrition and negative side effects of the bromocriptine (based on previous repeated measures fMRI studies and reports of bromocriptine, expected attrition is 4%-7%).

## E. Study Population

50 overweight/obese (25 < BMI < 35) adults ages 18-35 years of age. We will screen for enrollment such that 25 participants will have the DRD2 TaqIA A1 allele and 25 will have the A2/A2 variant. We will exclude participants who report current: a) contraindications of fMRI (e.g., metal implants, braces, or serious medical problems [e.g., known diabetes, CVD, recent stroke]), b) any previous habitual use of cigarettes or illicit drugs, or c) current major psychiatric disorders (depression, bipolar disorder, panic disorder, generalized anxiety disorder), d) pregnancy or breastfeeding e) current weight loss dieting and/or weight fluctuations great than 10 lbs in the previous 6 weeks. f) do not consume dairy e) allergy to bromocriptine, dairy, and nuts. Diabetes status will be assessed via self-report.

#### F. Study Procedures

#### 1. Screening Visit

At the screening visit, following consent, the potential participant will be weighed and height will be measured to ensure they are overweight (25 < BMI < 35). A brief screener for identifying MRI contraindications will be administered before inviting subjects to join the MRI portion of the

study, as done in prior fMRI studies. If participants satisfy inclusion and exclusion criteria during the screen, they will be scheduled for the testing assessments. Female participants will be asked to self-report the date of their last menstruation to ensure they are in the follicular phase and are not pregnant (pregnancy test will be offered). Saliva (genotyping) and blood glucose values (mg/dL) will be collected from consented participants at the initial screening appointment. (30 minutes)

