# 2. Testing Visits - Outline

At the Neuropsychology of Ingestive Behavior Lab

Baseline: Fasting blood draw, fasting drug or placebo administration

Baseline-60 minutes: Visual analogues scales (VAS) hunger and satiety, height and weight measurement, demographic and psychological surveys, waiting for drug to become active 60 minutes: Walk to Biomedical Research Imaging Center

At the Biomedical Research Imaging Center

90 minutes - 150 minutes: VAS hunger and satiety, MRI assessment, taste administration, resting state, anatomical scans

At the Neuropsychology of Ingestive Behavior Lab

150 minutes-180 minutes: VAS hunger and satiety, fixed milkshake consumption

180 minutes: Blood draw

180 minutes-210 minutes: Behavioral impulsivity, surveys

210 minutes: Blood draw

210-240 minutes: VAS ratings, hedonic ratings, ad libitum food intake

The testing visit will last approximately 4 hours. Testing visit occurs twice for each participant.

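### Pregnancy and breastfeeding are exclusions, but the only check described is at screening; none is described before the capsule at either testing visit

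*Protocol*

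**What the plan says.** Protocol section E makes the exclusion depend on what participants report: "We will exclude participants who report current" conditions, among them "d) pregnancy or breastfeeding".

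The check itself is in section F.1, Screening Visit. Women must "self-report the date of their last menstruation to ensure they are in the follicular phase and are not pregnant (pregnancy test will be offered". The test is offered, not required. That sentence comes directly after the statement that people who pass the screen move on: "they will be scheduled for the testing assessments".

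Dosing happens later. Section D says "For each participant, the study will include three visits on three separate days", and section C puts two weeks between the two testing visits. The outline in section F.2, which serves both testing visits, opens with "Baseline: Fasting blood draw, fasting drug or placebo administration" and mentions no pregnancy question, menstrual date or test.

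Section H notes that bromocriptine may weaken oral contraceptives and asks users to abstain or add another method for 24 hours. Section I bases its confidence in eligibility on screening having come before testing and randomization.

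**The concern.** Genotype is fixed, so checking it once at screening is enough. Pregnancy can begin, or be recognised, after screening. The plan names it as a reason not to take part, yet on the visible text it is last considered on a day before either dose, with no limit on how long before. A participant who had become ineligible could be given the capsule and scanned without anyone departing from the protocol.

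The design is within-subject, so every woman who completes it receives bromocriptine at one testing visit and is scanned at both. What is at stake is participant safety and consistent use of the plan's own exclusion. Sample size, power and analysis are not affected.

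**Working it through.** Neither document gives a figure on this point, so there is nothing to reproduce. Three checks were made.

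**1. Where a check is described**

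- Section F.1 (screening): menstrual date by self-report, test offered.
- Section F.2 (both testing visits): fasting blood draw, then capsule; no check listed.
- Section G, administration: collection of the capsule, blinding and hand-over; no check.
- Section G, Blood Draws, and SAP Exploratory Outcomes: the samples are for hormone assays; no pregnancy assay is named.
- Section H: contraception advice for oral-contraceptive users. This is a precaution, not a check.
- Section I: relies on screening.
- SAP: does not mention pregnancy or cycle phase.

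Count: one check at screening, none on the two testing days. The scan starts at 90 minutes (section F.2), so any question asked at the imaging centre would come after the capsule.

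**2. Whether the screening check could fall on a dosing day**

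It could not. Apart from the three separate days in section D, enrolment is by genotype ("We will screen for enrollment such that 25 participants will have the DRD2 TaqIA A1 allele and 25 will have the A2/A2 variant"), and the genotyping sample is taken at screening ("Saliva (genotyping) and blood glucose values (mg/dL) will be collected from consented participants at the initial screening appointment").

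**3. Whether follicular timing would cover both visits**

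Suppose the menstrual date is used to schedule testing.

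- From the documents: gap between testing visits, 14 days (section C).
- Assumed, because the documents give neither: cycle length *C* of 21 to 35 days and luteal length *U* of 12 to 14 days. The model describes natural cycles.
- Follicular days are 1 to *F*, with *F* = *C* − *U*. Visit 1 is on day *d*, from 1 to *F*. Visit 2 is on day *d* + 14.

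Visit 2 is follicular in two cases:

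- (a) same cycle: *d* + 14 ≤ *F*, so *d* ≤ *F* − 14;
- (b) next cycle already begun: *d* + 14 > *C*, so *d* ≥ *C* − 13. Since *d* ≤ *C* − *U*, this gives no days when *U* = 14 and two days when *U* = 12.

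Share of follicular visit-1 days for which visit 2 is also follicular:

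| Cycle (days) | *U* = 14 | *U* = 12 |
|---|---|---|
| 21 | 0/7 = 0% | (0+2)/9 = 22% |
| 25 | 0/11 = 0% | (0+2)/13 = 15% |
| 28 | 0/14 = 0% | (2+2)/16 = 25% |
| 30 | 2/16 = 12.5% | (4+2)/18 = 33% |
| 32 | 4/18 = 22% | (6+2)/20 = 40% |
| 35 | 7/21 = 33% | (9+2)/23 = 48% |

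Every entry is below one half. These are shares of possible visit-1 days, not of participants.

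The result depends on the gap. Over the same cycles and luteal lengths, the largest share stays at 48% for gaps of 14 to 16 days. It reaches 56% at 17 days (21-day cycle, *U* = 12). A 21-day gap gives 33% to 100%, and a 28-day gap with a 28-day cycle gives 100%.

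The same algebra limits the remedy. With *U* = 14, *d* + 14 ≤ *C*, so visit 2 always comes before the next menstruation is due. With *U* = 12, only the last two follicular days carry visit 2 past it. The last-menstruation date given at visit 2 would usually be the one that applied at visit 1.

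**The case against.** **The record is incomplete.** Section F.2 is headed as an outline, the consent pages are not available, and the prescreening material mentioned in section L is not shown. A pre-dose question may exist elsewhere. This stands as a limit: the point concerns the visible text, and a reader should not infer that the site makes no such check. Prescreening, however, precedes the screening visit and so cannot serve as a dosing-day check. The fuller sections G, H and I do not supply one either.

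**The menstrual date is probably there to time testing.** Nothing listed for the screening visit has a stated need for the follicular phase, and the sentence follows the one on scheduling. This is the more natural reading, and it gives visit 1 indirect protection. It does not usually reach visit 2 at a two-week gap. Scheduling visit 2 in the next follicular phase would need a new date, and none is described.

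**A reader might infer that follicular timing can never cover visit 2.** The documents do not support that. The 0% entries need a luteal phase of exactly 14 days, a cycle of 28 days or less and a gap of exactly 14 days. Section C does not say whether two weeks is exact or a minimum.

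**Repeating the check at visit 2 would find little.** Much of this stands. The menstrual date will often be unchanged, and a conception between the visits would be at most about two weeks old, which a test would mostly miss. The repeat check does more for the unlimited interval between screening and visit 1, and for a pregnancy recognised since the last contact.

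**Section I may mean only that eligibility is settled before randomization.** That is possible, but an earlier visit still cannot settle a condition that may begin afterwards.

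**Conclusion.** The point holds in limited form. Pregnancy and breastfeeding are exclusions. The visible text describes one check, at screening, and none before the capsule or scan on either testing day. That conclusion comes from reading the sections side by side and needs no assumption beyond the completeness of the text shown.

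The secondary statement, that follicular timing would usually leave visit 2 uncovered, rests on assumed cycles of 21 to 35 days, a luteal phase of 12 to 14 days and a gap close to two weeks. The share covered is then 0% to 48%.

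A reader might go further and infer that pregnant women are likely to be dosed, or that harm would follow. The documents give no pregnancy rate, no sex split and no pregnancy-specific risk for a single 1.6 mg dose or a scan, so neither can be claimed. This is a cheap improvement to safety procedure.

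**What to change.** Amend sections F.2 and I so that, before the capsule at both testing visits, staff:

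- ask about current pregnancy and breastfeeding;
- update the date of last menstruation;
- re-offer the pregnancy test already offered at screening.

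State that anyone who reports pregnancy or breastfeeding, or tests positive, is neither dosed nor scanned. The check has to be made at both visits, because the staff handing over the capsule are blinded and cannot limit it to the bromocriptine day.

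The cost is a few minutes and a test kit per visit, with an occasional cancelled visit. Very early conceptions, including most that occur between the two visits, would still be missed. If the site already does this, one line in each section is enough.

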# 2. Testing Visits - Outline

At the Neuropsychology of Ingestive Behavior Lab

Baseline: Fasting blood draw, fasting drug or placebo administration

Baseline-60 minutes: Visual analogues scales (VAS) hunger and satiety, height and weight measurement, demographic and psychological surveys, waiting for drug to become active 60 minutes: Walk to Biomedical Research Imaging Center

At the Biomedical Research Imaging Center

90 minutes - 150 minutes: VAS hunger and satiety, MRI assessment, taste administration, resting state, anatomical scans

At the Neuropsychology of Ingestive Behavior Lab

150 minutes-180 minutes: VAS hunger and satiety, fixed milkshake consumption

180 minutes: Blood draw

180 minutes-210 minutes: Behavioral impulsivity, surveys

210 minutes: Blood draw

210-240 minutes: VAS ratings, hedonic ratings, ad libitum food intake

The testing visit will last approximately 4 hours. Testing visit occurs twice for each participant.

## **G.** Study Evaluations and Measurements

#### Bromocriptine/placebo administration

Participants will be given either bromocriptine (1.6mg Cycloset) or placebo at each testing visit. Order of bromocriptine/placebo will be counterbalanced across the participants. The researcher and participant will be blinded to the treatment given. [name], [name], and IDS will have the randomization key. The research assistant will pick up the Cycloset or placebo from IDS. He or she will be blinded to the contents (whether placebo or Cycloset) and will give the participant the capsule to take orally. To allow the drug to reach maximum plasma concentration, participants will be scanned approximately 90 minutes following drug administration. The placebo will be developed by IDS and will come in a capsule which will look identical to the capsule the Cycloset is in.

#### **Blood Draws**

Each blood draw will occur in either the antecubital vein in the arm or in the cephalic vein in the hand. 6 mL of blood will be drawn three times. For each visit, the first blood draw (fasting) will occur at the start of the visit and the second and third will occur 30mins and 60mins after the fixed milkshake portion (after fMRI scan; see Fig 1). This will allow us to assess fasted

circulating hormone levels and gives us the ability to examine satiation hormone fluctuation over two time points that encompass the entirety of the previously characterized GLP1 peak in serum. A trained phlebotomist will perform the blood draws. The phlebotomist will try no more than 3 times unless the participant consents to further attempt. Blood samples for satiety hormones will be assayed using Bio-Plex Pro Human Diabetes 7-plex Assay (Bio-rad, Hercules, CA). This kit analyzes adiponectin, amylin, and GLP1. Additionally, a custom Human Cancer Panel 1 with only prolactin will be used to analyze prolactin concentrations (Bio-rad, Hercules, CA) using a Millipore Luminex (Darmstadt, Germany). All samples will be kept at -80° until processed. Our team is well versed in blood processing procedures and Luminex operation.

## Height and Weight

Height and weight will be measured without shoes or heavy clothing.

# Visual Analogue Scale

Visual Analogue Scales will be used to assess hunger, fullness, thirst, and nausea periodically throughout the testing visits. These will be distributed via iPad on Qualtrics software.

#### Neuroimaging Paradigms

Participants will complete 2 functional MRI paradigms: milkshake receipt paradigm and resting state paradigm, in addition to an anatomical scan. These paradigms examine different aspects of neural functioning. First, the milkshake receipt paradigm allows us to examine how the brain responds during exposure to a primary reward (receipt of highly palatable taste) and a tasteless control. Second, the steady state paradigm will allow for functional connectivity analyses to examine reward and behavioral differences in the brain at 'rest'.

#### Milkshake receipt fMRI paradigm

The paradigm is controlled by in-house Python scripts. Each trial in the paradigm starts with the presentation of a cue (duration: 1s) signaling the impending delivery of either 3 mL of highly palatable milkshake or a control water solution over a period of 6s. Taste delivery is followed by a 1s wait period and 2s rinse (tasteless solution). The next trial begins after a 1-9s jitter. Order of milkshake and water trials is pseudo randomized. In total, there are 32 trials per run for a total of 2 8-minute runs. This paradigm allows us to assess brain response to a receipt of primary reward (milkshake) and control (water solution) as well as in vivo neuroadaptations over repeated exposures.

#### Resting state functional connectivity

We will use resting state fMRI data for functional connectivity analyses to provide data about brain functioning and connectivity. Functional connectivity is assessed by examining the correlation of fluctuations of BOLD signals in different regions of the "resting" brain and is thought to provide a measure of its functional organization Steady-state fMRI data will be acquired in one run of 5 minutes; participants will be asked to remain still and relaxed and stay awake during the scanning. This paradigm allows us to assess the brain's functional connectivity. We hypothesize that connectivity from the hypothalamus will be significantly altered by bromocriptine.

Total scan time will be approximately 50 minutes.

#### Behavioral impulsivity task

We will use a basic stop-signal task that assesses behavioral inhibitory control in response to palatable food images, adapted from Batterink and colleagues (12) and in current use in our lab. This task requires subjects to respond to "go" signals and occasionally inhibit responses to "nogo" signals. It measures the ability to inhibit a pre-potent tendency to respond. The task consists of 80 trials, evenly split between left-button responses (the letter A) and right-button responses (the letter Z). 16 total stop trials are presented (the stop signal is the letter X). The stop signal delay begins at 200ms, and increments by one screen refresh period depending on trial performance. The number of responses to stop signal stimuli (commission errors) will be used to provide a behavioral measure of inhibition failure.

## Ad lib taste test

After the fMRI scan and fixed consumption of milkshake, participants undergo the postprandial blood draw and perform a taste test which includes perceptual hedonic ratings of a variety of foods and an ad lib intake challenge. Participants first perform a taste test of 1g of each of the 4 foods (M&Ms, Skittles, Doritos, cheddar popcorn). These foods were selected as they are generally considered highly palatable and represent a variety of flavors, mouth feels and nutrient contents (e.g., sugar, fat, salt). Participants complete perceptual hedonic ratings of the pleasantness, sweetness, taste intensity, and desire to consume on generalized, labeled magnitude scales of each of the foods. After the taste test, participants will be told that they are free to eat as many snacks as they like, as we have to discard them after each participant (they will not be allowed to have backpacks, purses, or bags, so they do not take snacks from the room). Participants will be left alone during the tasting to minimize demand characteristics. Food will be pre- and post-weighed to determine ad lib intake. Total caloric intake will be calculated and translated to % of calorie needs using gender-specific formulas (NAS, 2005). We currently use these techniques (NORC5-34387, HHSN275201300015C).

